7.1.9 End of Study Visit or Early Termination Procedures

The following information will be collected and procedures or evaluations will be performed at the final visit (in-facility after completion of the Unassisted Home Evaluable Period):

- Patient Reported Outcomes (collected during Week 6 of Unassisted Home Evaluable Period or following Early Termination)
- Physical exam including weight
- Vital signs
- 12-lead ECG
- Adverse events/serious adverse event/adverse device effect
- Concomitant medications
- Clinical laboratory evaluations as specified in Table 2
- Device-related product issues (device-related product complaints)
- Device related AEs and SAEs will be followed post-study until resolution

If a subject discontinues from the study prematurely, every attempt should be made to perform all of the procedures and evaluations that are scheduled for the final visit (i.e., End of Study Visit). Upon exiting the study, subjects who discontinued early will be transitioned to a conventional HD device. HemoCareTM Hemodialysis System used for these subjects will be removed from their home.

For subjects who successfully complete the study, the site should schedule the End of Study Visit to coincide with the Qualification Visit of the Extension Study (DKPL-00674-001: An Open Label Study to Allow Patients Continuous Use of the HemoCareTM Hemodialysis

System for Home Hemodialysis Prior to Market Authorization), to allow for seamless enrollment and continued access to the HemoCareTM Hemodialysis System in the home.

7.2 Study Activities

7.2.1 Enrollment

A subject will be considered enrolled in the study on the date the Investigator or designee confirms all inclusion criteria are met, no exclusion criteria are present, the subject's residence is capable of hosting the HemoCareTM Hemodialysis System, and informed consent has been obtained. This confirmation may be documented in writing (via the Enrollment Approval template) or electronically (via a medical record entry or by email with signature and date/time stamp).

7.2.2 Demographics and Baseline Characteristics

A complete medical history will include a review of all major body systems and medical history, as applicable. Information regarding the type and frequency of dialysis therapy received prior to enrollment in this study and type of access will be obtained.

Demographics will include the age, gender, race, and ethnicity.

7.2.3 Physical Examination

Physical examinations will be performed during Screening, Assisted Evaluable Period Visit 1, Unassisted Evaluable Period Visit 2, and at End of Study visits.

Any new condition or worsening of a pre-existing condition from Screening will be noted and recorded on the AE eCRF page. Height will be measured at Screening only.

Weight will be measured at Screening and at the End of Study visit. Additional collection of pre- and post-treatment weights will occur as noted in Section 7.10.

An attempt should be made to perform a final physical examination on subjects who complete Screening and enter the study, but who discontinue from the study early, particularly if the subject is discontinuing from the study because of an AE.

7.2.4 Vital Signs

Vital signs will include measurements of height, weight, sitting blood pressure, sitting respiratory rate, temperature, and sitting pulse rate. Vital signs will be obtained at Screening, Assisted Evaluable Period Visit 1, Unassisted Evaluable Period Visit 2, and at the End of Study visit. Additional vital signs will be collected during treatment times and are explained in Section 7.10, Clinical Observations.

7.2.5 Electrocardiogram

A 12-lead electrocardiogram (ECG) will be performed during Screening and the End of Study visit. The 12-lead ECG will be performed after the subject has been resting in a supine position for 5 minutes. Any abnormal findings will be recorded and abnormal changes from the Screening ECG will be considered AEs.

7.2.6 Kt/V

Weekly stdKt/Vurea will be calculated from pre- and post-dialysis urea levels during each evaluable period. Blood samples will be obtained every two weeks during each Evaluable Period. A central laboratory will be used for the analysis of the blood samples. If the weekly stdKt/Vurea goal is not met, the reason will be recorded.

Study personnel will be trained to obtain the pre- and post-treatment blood samples based on the Kidney Disease Outcome Quality Initiative Guidelines for sample collection.

7.3 Reliability of HemoCareTM Hemodialysis System

Treatments will be classified as either complete (receiving at least 90% of planned treatment time), incomplete (receiving less than this), or missed altogether. Planned treatment will be defined as the treatment time selected and confirmed by the user at the start of each treatment. For all incomplete and missed treatments, the Medical Professional will record a reason in the eCRF.

7.4 Training on HemoCareTM Hemodialysis System and Study Procedures

7.4.1 Study Site Team Training

The assigned site team members (investigators and nurses) will be trained on HemoCareTM Hemodialysis System by the Sponsors (or designee) as part of site initiation. HemoCareTM Hemodialysis System training tools developed specifically for use with HemoCareTM Hemodialysis System will be utilized. Assigned site team members will be required to complete and pass a skill assessment before they are approved to train enrolled subjects at their site. The skill assessment includes the Nurse Skills Checklist and the Nurse Final Knowledge Check.

All assigned site team members will also receive study training specific to their study role (e.g., protocol, eCRF, laboratory procedures) prior to starting study activities.

7.4.2 Subject and Care Partner Training

Enrolled subjects and care partners will receive training during the In-Facility Introduction Period as specified above. Approved site training nurses will conduct all subject and care partner training utilizing HemoCareTM Hemodialysis System training tools. Enrolled subjects and care partners will be required to demonstrate competency of a skills assessment commensurate with their responsibilities as defined in the care plan in order to complete the In-Facility Introduction Period.

7.6 Patient Reported Outcomes

Clinical outcomes will be documented as part of objective clinical assessment. Patient reported data will be collected as shown in Table 4.

Table 4. Patient Reported Outcomes

Patient Reported Outcomes (PRO)	Collection Time Point						
	Screening Period	In-Facility Introduction Period	Transition Period A	Assisted Evaluable Period	Transition Period B	Unassisted Evaluable Period	End of Study Visit
Renal Treatment Satisfactory Questionnaire (RTSQ)		X		X		X	X
Patient Recovery Time Questionnaire		X		X		X	X
Zarit Burden Interview (ZBI- 12)		X		X		X	X

[figure not shown]
Trial subjects and/or care partners will complete patient reported outcomes (PROs) independently and the completed questionnaires will be transferred into the Electronic Data Capture (EDC) system. Study sites will be instructed to review the completed questionnaires and follow up with the study subjects if necessary based on their responses.

7.7 Ultrafiltration

HemoCare™ Hemodialysis System calculates fluid removal based on the subject's starting weight, target weight, prime and rinse back volume, and any additional fluid adjustments made by the user. Ultrafiltration (UF) removed is the total volume of fluid removed during a dialysis treatment. Fluid weight removed is total UF removed minus prime and rinseback volumes and any fluid adjustments. Target weight is the goal weight prescribed for a given treatment. Starting weight is the weight of the subject pre-treatment. The UF goal is the difference between the starting weight and target weight, with the addition of prime and rinseback volumes, and any fluid adjustments (such as oral intake during treatment).

In addition, the subject's weight will also be measured before and after each treatment and recorded in the device. Calibrated digital scales will be provided. Subjects will measure their pre- and post-dialysis weight. Subjects will record the volume or weight of any fluid they plan to

consume during treatment. Subjects will be encouraged
to restrict output to before pre-treatment weight or after post-treatment weight (where possible).
To minimize variability in this measurement, clinic staff and subjects will be instructed to use a digital scale and the same scale for all study treatments and to standardize clothes and shoes worm by the subject at the pre-dialysis and post-dialysis weighing. All training, supplies, and techniques utilized by the subject during the Assisted Evaluable Period must be similarly utilized during the Unassisted Home Evaluable Period.

CONFIDENTIAL DEKA R&D CORP. CVS KIDNEY CARE During both Evaluable Periods, the user will be limited in the UF adjustments they can make at the start of and during treatment. Prior to treatment and during treatment, the user can adjust UF goal and treatment time within ranges pre-set by the Investigator.

Clinic staff and subjects will be trained to assess and respond to situations regarding fluid balance as they may occur during treatments.

The target weight will be determined by the clinician through a careful physical exam, a focused history for symptoms of recent volume overload or volume depletion, and a review of previous dialysis sessions.

If the subject is more than 1kg above or below

the target weight, the site will obtain the reason/narrative for this discordance. Possible reasons may include output not accounted for, oral intake not accounted for in the UF goal, improper weighing techniques, or unknown. Sites will discuss and document these responses with the subjects during their regular communications and transcribe a reason or reasons for the discordance in the applicable eCRFs as appropriate.

7.8 Control of Serum Phosphorus and Serum Potassium

Investigators will receive a notification per subject from the central laboratory for any of the following results:

- Any post-dialysis serum phosphorus level >5.5 mg/dL
- Any post-dialysis serum phosphorus level <2.2 mg/dL
- Any post-dialysis serum potassium level of <3.5 meq/L
- Any post-dialysis serum potassium level of >5.9 meq/L

Investigators will be instructed to follow up with their subjects regarding the specific result if clinically significant and treat the subject per their local standard of care guidelines. Investigators should also report any AEs (if applicable) using the guidance listed in Section 8. Additionally, investigators/designees will document what action was taken (if necessary) to address any alert values.

7.10 Clinical Observations

Each time a subject is dialyzed with HemoCare[™] Hemodialysis System, the following information will be obtained from HemoCare[™] Connectivity Platform Treatment Flowsheet (Section 7.11):

- Medications given during or immediately after treatment
- Anticoagulation regimen
- Treatment interventions
- Patient weight: pre- and post-dialysis (if unable to enter post-dialysis weight in device, subject will note the weight on the Treatment Flowsheet)
- Blood pressure: both pre and post-dialysis seated, or both pre-dialysis and post-dialysis standing
- Pulse: both pre-dialysis and post-dialysis seated, or both pre-dialysis and post-dialysis standing
- Body temperature: pre- and post-dialysis

A study nurse or their designee will collect study data weekly (minimum) as detailed in the section below. The Investigator or designee will assess each subject on a weekly basis according to care plan (see Section 7.11). The assessment may include blood pressure, fluid status, and dialysis prescription.

7.11 Treatment Flowsheet and Weekly Assessment

At every treatment with HemoCare™ Hemodialysis System (excluding In-Facility Introduction Period), subjects will complete Treatment Flowsheet to document certain data. In addition, the Investigator or designee will perform a weekly assessment of each enrolled subject. Sites may choose to communicate more frequently with the study subjects per local requirements or standard-

of-care. At a minimum, the Investigator or qualified designee must communicate with the subject weekly to review and discuss the following:

- Subject status/condition updates potential AEs experienced
- Treatment interruptions
- Confirmation if the subject contacted the dialysis center for support with a device or health related issue
- Confirmation if the subject was able to sleep during treatment and duration of sleep
- Treatment outcome
- Confirmation if the subject altered their treatment parameters within the range(s) allowed by their Investigator
- Ultrafiltration details unaccounted for output or oral intake
- Document completion of study requirements (e.g., PROs).
- Any changes to current medications, including those taken since the last Weekly Assessment
- Current treatment inventory needs, including any components with expiration dates coming up

The site staff will use this data along with the HemoCareTM Connectivity Platform treatment data to monitor the subject. This data will serve as supplemental source documentation for the sites to support consistent data collection during Evaluable Periods.

Sites may choose to communicate more frequently with the study subjects per local requirements or standard-of-care. At a minimum, the Investigator or qualified designee must communicate with the subject weekly to review. Based on all data collected from the subject, the site staff will complete their source logs and eCRFs as appropriate.

Il prescription changes will be documented in source documents.

7.12 Water and Dialysate Sampling Analysis

HemoCare™ Water Device shall not produce water that exceeds the chemical contaminant levels as stated in the ANSI/AAMI 13959:2014 standard.

The Sponsor or its designee will train the person(s) responsible for collecting the water and dialysate samples during the study. Instructions will be provided in the study training materials. Standardized recovery methods and positive and negative controls will be incorporated into the testing protocol(s). A central laboratory will be used for all water and dialysate testing.

Sample results will be sent to the study sites and Sponsor for real time review and action (if appropriate). Observations and decisions regarding corrective measures (e.g., re-culture, consumables replacement, and/or disinfection of either device) will be based on the organism

growing, whether or not bacterial or endotoxin levels exceed the specified guidelines, and any clinical symptoms the subject may have. A Safety Management Committee will also review study wide results per the Safety Management Plan to search for trends and to action appropriately.

[figure not shown]
Analysis of water and dialysate will be performed on samples obtained as follows.

7.12.1 Chemical Contaminants - Tap Water

Samples of tap water will be collected by Sponsor or designees and tested for chemical contaminants from each study site during site feasibility, prior to HemoCareTM Hemodialysis System installations at the site. Samples will also be collected during home assessments, prior to device installation, while consented trial subjects are in the screening period. Source water needs to be of US EPA drinking water quality.

Additional tap water samples will be collected and tested from all actively participating locations, at a minimum, yearly or as required by site policy or local regulations. Excluding yearly retesting, trial subjects cannot treat on HemoCareTM Hemodialysis Systems in these locations until the results are received and reviewed by the trial site and Sponsor.

7.12.2 Chemical Contaminants – HemoCare™ Hemodialysis System

Post ultrafilter water samples shall not exceed chemical contaminant levels as stated in the ANSI/AAMI 13959:2014 standard for dialysis water.

7.12.3 Microbiological Cultures – Incoming Source/Feed Water

Incoming source/feed water will be collected by sponsor personnel or designees at site assessment or installation, both in-center and at the trial subjects' homes, and tested for microbial levels.

These samples will be collected from the incoming source/feed water. Trial subjects cannot treat on HemoCareTM Hemodialysis System in these locations until the results are received and reviewed by the trial site and Sponsor.

Source water needs to be < 500 CFU/mL for microbial levels.

7.12.4 Microbiological Cultures and Endotoxin – Ultrapure Water or Dialysate

[figure not shown]
Ultrapure, post ultrafilter samples from HemoCare™ Hemodialysis System (water or dialysate) will be collected from the device by sponsor personnel or designees at installation, both in-center and at the trial subjects' homes, and tested for microbiological and endotoxin levels. At each sample collection time point, 2 ultrapure samples will be collected. Both samples will be collected and packaged using aseptic techniques, sent to the central lab for analysis, and analyzed independently, but concurrently.

rial subjects cannot treat on HemoCare™ Hemodialysis System in these locations until the results are received and reviewed by the trial site and Sponsor.

If subsequent in-center installations are required (e.g., after initial device installation is complete, a second device is installed at the same clinic), new ultrapure installation samples will be collected. The subject cannot treat on the newly installed device until the results are analyzed and reported. Once a HemoCareTM Hemodialysis System has been installed and passes the ultrapure microbial and endotoxin analysis, any replacement device (e.g. replacement treatment device or water device) will not require ultrapure samples to be recollected unless source water has changed.

Ultrapure samples (water or dialysate) produced by HemoCare™ Hemodialysis System shall not exceed microbial or endotoxin levels as stated in the ANSI/AAMI/ISO 23500-5:2019 standard. Based on this standard, the acceptable limit for microorganisms is < 0.1 CFU/mL and the acceptable limit for endotoxin is < 0.03 EU/mL

7.12.6 Process for Responding to Out-of-Specification Results

7.12.6.1 Decision Tree

Clinical study decision trees for ultrapure have been developed and will be provided to study sites. These decision trees provide guidance to the clinical site and the DEKA R&D Corp. and CVS Kidney Care team on appropriate actions to be taken in situations where out-of-specification (OOS) results are received from ultrapure

Upon confirmation of an OOS value for either endotoxin or bacteria, the user will be directed to replace the consumable portions of the device

Additional actions may include:

- All device logs evaluated for anomalies
- Aseptic procedure checklists recorded during sample collection and processing reviewed for anomalies
- Contract Laboratory will conduct an investigation of their procedures and processes for any OOS endotoxin or micro-organism result
- Consideration for additional actions such as retrieval and analysis of hardware and/or disposables, on site investigation for additional machine and environmental cultures, etc.

7.12.6.3 Endotoxin Out-of-Specification Analysis – Ultrapure

After an OOS value is recorded on the first aliquot volume tested from the primary tube, a test will be performed on a second aliquot that will be independently diluted, to eliminate any contamination that might have been introduced during the first aliquot dilution step. If this retest confirms an OOS value, the root cause investigation will continue to identify a probable cause of the endotoxin. The Secondary Tube will be assayed as part of the root cause investigation.

7.12.7 Chloramine, pH, and Conductivity Testing

Chloramine testing of the water for dialysis will be done prior to each dialysis treatment.

8 Adverse Events reporting

An AE is any untoward medical occurrence in a subject administered by a study product and which does not necessarily have a causal relationship with the treatment or study product.

An AE can therefore be any unfavorable and unintended sign (including an abnormal laboratory function), symptom (e.g., rash, pain, discomfort, fever, dizziness, etc.), disease (e.g., bacteremia, pancreatitis, etc.) or outcome of death temporally associated with the use of the study product, whether or not the event is considered to have a causal relationship with the study product.

Laboratory and vital sign abnormalities qualify as AEs if medical intervention is required to treat or address the abnormality, if the subject must be discontinued from the study due to the abnormality, or if the value exceeds specific limits defined by the protocol as qualifying it as an AE.

An elective procedure/surgery that occurs during the course of a study, but is being performed for a documented pre-existing condition and was pre-planned prior to study entry will not qualify as an AE. If, however, the pre-existing condition unexpectedly deteriorates during the study requiring the procedure/surgery to be performed earlier than planned, the condition for which the procedure/surgery is being performed will qualify as an AE.

Adverse events will be collected starting from the time of enrollment until the end of participation in the study. If an AE occurs, a full description of the event should be recorded including the date of onset, severity, time course, description, actions taken, and causal relationship of the AE to the study product(s). Investigators should review and reference the Causality definitions below when determining relationship of the AE to the study product. The investigators may also discuss the event(s) with the Medical Monitor, but the Investigator must make, document and report the relationship for every AE. All AEs must be documented in source documents and on the eCRFs, no matter how common they are for a particular subject and regardless of the causality assigned by the Investigator.

The process for the collection of subject reported events will be the same for both Evaluable Treatment periods. Raw events will be collected through the Weekly Assessments, as well as routine medical record review and standard of care communications with the subject and/or care partner.

All AEs and SAEs, regardless of relatedness, should be recorded.

Additionally, any AE voluntarily reported by the subject should be recorded and verified by the Investigator or designee on the appropriate source documents and eCRF pages.

The outcome/resolution of all AEs and SAEs will be determined by the Investigator and documented on the AE eCRF. Investigators will be instructed to follow all AEs/SAEs as follows: Unrelated AEs will be followed until resolution or until the end of the study whichever occurs first. Adverse device effects (related AEs) and all SAEs (related or not) will be followed until resolution or stable, including following the subject after the end of the study if necessary. The outcome categories that can be chosen on the eCRF by the Investigator include: Fatal, not recovered/not resolved (this outcome is reached for AEs which are ongoing when the subject's end of study is due to death related to another AE), Recovering/Resolving (this outcome is reached for AEs which are ongoing at the subject's end of study), Recovered/Resolved with Sequelae (if there are some residual effects caused by the event), Recovered/Resolved, and Unknown.

All SAEs regardless of their relationship to the study product will be submitted to Sponsor or designee by the Investigator or designee within 24 hours of becoming aware of the event. If an investigator becomes aware after study completion of an SAE that occurred in a subject during their participation in the study, the SAE must be reported on the SAE Form within 24 hours after awareness. Serious adverse events occurring within 30 days of study completion (per subject) will also be reported.

An AE can result from the use of the study product in accordance with the protocol, as well as from an accidental or intentional misuse of the study product or any other treatment error such as unintentional administration or use of another product during the course of the study.

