5.3 Subject Discontinuation/Withdrawal

Subjects may be withdrawn/prematurely discontinued from the study if their participation is discontinued before completion of the Unassisted Evaluation Period. The reason(s) could include:

- 1. Adverse event(s) (AEs)
- Inadequate dialysis
- 3. Protocol violations (i.e., the subject failed to meet protocol entry criteria or did not adhere to the protocol requirements)
- 4. Pregnancy, lactating or not using medically acceptable means of contraception (confirmed by Investigator)
- 5. Lost to follow-up (i.e., subject fails to return for study visits)
- 6. Voluntary withdrawal (i.e., subject's request)

- 7. Termination of the study
- 8. Investigator's discretion
- 9. Renal transplantation
- 10. Switch to Peritoneal Dialysis (PD)
- 11. Subject death
- 12. Other reason (with reason noted on the electronic case report form [eCRF])

The Investigator may terminate a subject's study participation at any time during the study if he/she judges it to be in the subject's best interest. In addition, a subject may discontinue his or her participation at any time during the study. If a subject's participation is discontinued, the reason(s) must be recorded in the source documents and on the eCRFs. If a subject discontinues for any reason, every effort should be made to perform all of the procedures that are scheduled for the last visit. In addition, adverse device effects (ADEs) and all serious adverse events (SAEs), related to study treatment or not, will be followed post-study by the Investigator until the subject is stable or the situation is resolved.

Discontinued subjects will not be replaced unless the targets for enrollment/treatments will not be achieved with the current active group of study subjects. The Investigator or designee should inform their site monitor the moment any subject is discontinued from the study.

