8.2 Adverse Event Reporting

8.2.1 Reporting Adverse Events to Sponsor/Designee

During the course of the study, the Investigator or designee will routinely monitor each subject for the occurrence of any AE/ADE. If an AE/ADE occurs, the Investigator or designee will complete the AE eCRF which includes the following:

- Description of the event
- Start and stop date of the event
- Timing of the event (prior to first study treatment, during treatment set-up, during treatment, within 4 hours after treatment ends, > 4 hours after treatment ends)

[figure not shown]

- Seriousness of the event (yes, no) (assessed by PI or Sub-I)
- Severity of the event (mild, moderate, or severe) (assessed by PI or Sub-I)
- Causality of the event (related to treatment and/or related to the device) (assessed by PI or Sub-I)
- Action taken
- Outcome of the event (fatal, not recovered/not resolved, recovered/resolved with sequelae, recovered/resolved, and unknown)

All SAEs must be reported to the Sponsor/designee within 24 hours of the Investigator or designee becoming aware of its occurrence. The informed site team member should also contact their site monitor by phone or email to notify him/her of the event. This requirement is irrespective of whether the AE is thought to be possibly related to the study product or not. Expedited Reporting of Serious Adverse Events and Suspected Unexpected Serious Adverse Reaction (SUSAR). Sponsor/designee will assess each SAE reported by the Investigator to determine if the SAE qualifies as an expedited report according to FDA criteria. Sponsor/designee will report to FDA according to the applicable time requirements.

Per regulations, when an Unexpected Adverse Device Effect (UADE) or SUSAR occurs Investigators will receive a letter from Sponsor/designee describing the UADE/SUSAR. The Investigator should file this letter within their Investigator Study Binder. Additionally, the expedited report letter should be submitted by the Investigator to their IRB/REB, as appropriate per FDA regulations.

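### For AEs still ongoing at end of study, Section 8 sets the outcome by how participation ended rather than by the AE's status, and the Section 8.2.1 list omits the category it assigns

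*Combined protocol and SAP*

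**What the plan says.** Section 8 (Adverse Events reporting) leaves the outcome of each AE to the Investigator and introduces its list with "The outcome categories that can be chosen on the eCRF by the Investigator include". The list has six entries: fatal, not recovered/not resolved, recovering/resolving, recovered/resolved with sequelae, recovered/resolved, and unknown. Two of them cover an AE that has not ended:

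- The first is *not recovered/not resolved*, which Section 8 explains in these words: "this outcome is reached for AEs which are ongoing when the subject's end of study is due to death related to another AE".
- The second, *recovering/resolving*, is given as "Recovering/Resolving (this outcome is reached for AEs which are ongoing at the subject's end of study".

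Section 8.2.1 describes the same form ("the Investigator or designee will complete the AE eCRF which includes the following") and gives the outcome item as "Outcome of the event (fatal, not recovered/not resolved, recovered/resolved with sequelae, recovered/resolved, and unknown". That is five entries.

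Section 8 also sets how long events are followed. For unrelated events: "Unrelated AEs will be followed until resolution or until the end of the study whichever occurs first". Adverse device effects and all SAEs "will be followed until resolution or stable, including following the subject after the end of the study if necessary". Section 5.3 says much the same about device effects and SAEs in subjects who discontinue, and names adverse events as the first possible reason for discontinuation.

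**The concern.** The names of the two ongoing categories describe a clinical course: not getting better, or getting better. Their definitions describe something else, namely whether the subject's participation ended in death from another AE. Take a subject who withdraws because an AE persists or worsens. The subject is alive and the event is ongoing, so the Section 8 definition sends it to *recovering/resolving*. The same happens to an unchanged AE in a subject who completes the study normally.

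The category that Section 8 assigns to these events is also the one that Section 8.2.1 leaves out. Anyone building or completing the form from Section 8.2.1 has to choose between *not recovered/not resolved*, against the Section 8 definition, and *unknown*, although the status is known.

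What is at stake is the accuracy of the AE outcome field. Under Section 8 the error runs in one direction: unresolved events are recorded as recovering.

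**Working it through.** No formula applies, and the plan gives no figure to reproduce. The check sets the two outcome lists and the follow-up rules side by side.

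**Step 1: count the categories.** Section 8 has 6 and Section 8.2.1 has 5; 6 − 5 = 1. The missing one is *recovering/resolving*. The Section 8.2.1 item is a complete parenthesis with no gap or redaction in it.

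**Step 2: run typical cases through each list.**

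| AE at the end of follow-up | Section 8 definitions | Section 8.2.1 list |
|---|---|---|
| Ongoing; subject dies of another AE | Not recovered/not resolved (also meets the literal definition of recovering/resolving) | Not recovered/not resolved |
| Ongoing and improving; subject alive | Recovering/resolving | No matching option; not recovered/not resolved or unknown |
| Ongoing, unchanged or worsening; subject alive | Recovering/resolving | Not recovered/not resolved or unknown |
| Device effect or SAE, stable but unresolved after post-study follow-up | No fitting category | Not recovered/not resolved, by its name only |

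The third row is the substantive error. The second and third rows together are the conflict between the sections. The first row shows that the Section 8 definitions overlap, because death from another AE is itself an end of study.

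**Step 3: see how long the label lasts.** Follow-up of unrelated, non-serious AEs stops at end of study, so their label is final. Device effects and SAEs are followed until resolved or stable, so an outcome entered at exit can be updated. However, *stable* is an accepted end of follow-up that no Section 8 definition matches unless the event has also resolved.

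**Step 4: see which analyses use outcome.** The primary safety model in Section 9.4.1 takes the number of AEs with the log of the number of treatments as offset. The AE summaries and tests in Section 9.5 use system organ class, preferred term, anticipated or unanticipated status, seriousness, device-relatedness and severity. None of them uses outcome. Section 9.8 refers to the SAP for further AE analyses without describing them.

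**The case against.** The strongest reply is that little depends on this field. The rate ratio counts an AE whatever its outcome, and the secondary tables do not tabulate outcome. Device effects and SAEs, the events of most concern, are not closed at exit. The form also records stop dates, severity and action taken, so an analyst can still see that an event was ongoing; only the distinction between improving and not improving is lost. The Investigator determines the outcome, the list is introduced non-exhaustively, and *unknown* is available. The options that sites actually see depend on the eCRF as built, which is not among the documents, so divergence between sites is not established.

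Most of this stands, and it limits the point to a minor one. It does not remove it. Discretion does not undo a stated definition that calls an unchanged or worsening event recovering, and the two lists cannot both describe the same form.

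Three stronger readings are tempting, and the documents do not support them:

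- A reader might infer that the clinical safety determination in Section 9.2 is compromised. That section rests it on the rate and type of AEs, not on their outcome.
- A reader might infer that no surviving subject can ever have an AE recorded as not recovered. That holds only if Section 8 is applied literally and Section 8.2.1, which offers the category without restriction, is ignored.
- A reader might size the problem from attrition, since up to 70 subjects may enrol so that about 30 enter the Unassisted Home Evaluable Period. That difference counts subjects leaving for any reason against an enrolment ceiling. It does not count ongoing AEs, and AEs ongoing at normal completion are affected too.

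**Conclusion.** The point holds for AEs still ongoing when a subject's participation ends, whether by withdrawal or by normal completion. For those events Section 8 assigns the outcome by the manner of exit, and Section 8.2.1 contradicts Section 8 on which outcomes the form offers. Fatal, recovered, and recovered with sequelae do follow the event's own status and are not in question.

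Severity is minor. The effect is confined to recorded AE outcomes, which would overstate recovery if Section 8 is applied as written. It is lasting mainly for unrelated, non-serious AEs, with a residual gap for device effects and SAEs that end stable and unresolved. The documents do not allow the number of affected events to be estimated. The conclusion assumes that both sections describe the one AE eCRF, as their wording indicates, and that no SAP analysis outside the text reviewed uses outcome.

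**What to change.** In Section 8, define *not recovered/not resolved* as ongoing without improvement at the last assessment, and *recovering/resolving* as ongoing and improving at the last assessment, in both cases whatever the reason for end of study. For device effects and SAEs followed beyond exit, the last assessment is the last post-study one, so a stable, unresolved event then has a category. Put the same six-item list in Section 8.2.1 and in the eCRF.

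The cost is two sentences in Section 8, one added item in the Section 8.2.1 list and, if the form was built from that list, one pick-list entry. No visit, treatment or planned analysis changes. The downside is that sites must judge at the last contact whether the event is improving.
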